### ***Additional supportive analysis for splenomegaly-related scores domains***

The symptom domain score will be calculated based on the first three questions in the splenomegaly-related score questionnaire (abdominal discomfort, satiety and pain under the rib). The 7-day mean of the daily sum of scores of these three questions will be defined as the symptom domain score. The impact domain score will be calculated based on the last two questions (bending down, body image). The 7-day mean of the daily sum of scores of these two questions will be defined as the impact domain score. The 7-day mean of the daily scores of each question in the splenomegaly-related score questionnaire will be defined as the score for each question. The change from baseline to Week 52 in these two domain scores and each question in the splenomegaly-related score questionnaire will be analyzed using the MMRM, similarly to the primary analysis of SRS.

### ***Additional supportive analysis for DLco and spleen volume (MN)***

To evaluate the treatment effect on the absolute change on DLco (% predicted) and spleen volume (MN), the change from baseline on these two endpoints up to Week 52 will be analyzed using an analogous MMRM model.

### **2.4.5.2 Analyses of secondary efficacy endpoints**

#### ***Liver volume***

The MMRM model as used in the primary analysis of spleen volume under primary efficacy endpoints will be used to compare treatment groups for percentage change in liver volume from baseline to Week 52, using mITT population. Supportive summary in mITT-C population will be provided. Sensitivity analyses are not planned, but may be undertaken if necessary.

#### ***Platelet counts***

The MMRM model as used in the primary analysis of spleen volume under primary efficacy endpoints will be used to compare treatment groups for percentage change in platelet count from baseline to Week 52, using mITT population. Data collected at the quarterly visits will be included in the MMRM model. Supportive summary in mITT-C population will be provided.

#### ***BFI scale - Item 3***

The MMRM model as used in the primary analysis of spleen volume under primary efficacy endpoints will be used to compare treatment groups for BFI - Item 3 – for change from baseline to Week 52, using mITT population. Supportive summary in mITT-C population will be provided. Sensitivity analyses are not planned, but may be undertaken if necessary.

#### ***BPI scale - Item 3***

The MMRM model as used in the primary analysis of spleen volume under primary efficacy endpoints will be used to compare treatment groups for BPI - Item 3 – for change from baseline to Week 52, using mITT population. Supportive summary in mITT-C population will be provided. Sensitivity analyses are not planned, but may be undertaken if necessary.

#### ***FACIT-Dyspnea symptom score***

The MMRM model as used in the primary analysis of spleen volume under primary efficacy endpoints will be used to compare treatment groups for FACIT-Dyspnea symptom score, change from baseline to Week 52, using mITT population. Supportive summary in mITT-C population will be provided. Sensitivity analyses are not planned, but may be undertaken if necessary.

#### ***Splenomegaly-related score***

This is part of primary endpoints in US; all analyses for this endpoint are described in [Section 2.4.5.1](#).

The summary plots of the LS means from the MMRM for all the secondary efficacy endpoints in change or percentage change from baseline up to Week 52 with 95% CIs will be provided.

### **2.4.5.3 Multiplicity issues**

#### ***Primary endpoints***

The hypothesis testing of the primary endpoints will proceed as follows:

- Compare olipudase alfa to placebo on DLco and spleen volume. The overall 5% significance level for the two hypothesis tests will be maintained using the Hochberg method [MTP2 is maintained for 2-sided, 2-endpoint testing(20)]:
  - Higher of the two p-values will be compared to 0.05; if this  $p < 0.05$ , both DLco and spleen volume are significant.
  - If higher p-value  $\geq 0.05$ , and lower p-value  $< 0.025$ , then the endpoint associated with lower p value is significant but one associated with higher p value is not significant.

For Europe and ROW: from the sponsor perspective, the study will be declared positive if at least one of the primary endpoints is statistically significant by the above method.

For US only: If spleen volume is statistically significant based on the above testing, comparison of olipudase alfa versus placebo on SRS will be considered; if the two-sided p-value is  $< 0.15$ , then the combination spleen endpoint is considered significant. Otherwise, the combination spleen endpoint is not significant. From the sponsor perspective, the study will be declared positive if either DLco or combination spleen endpoint is significant.

#### ***Secondary endpoints (sequential testing)***

If statistical significance is reached on **both** the DLco and spleen volume using the Hochberg method (and the trend in splenomegaly-related score is established in case of USA), then hypothesis testing of the secondary efficacy endpoints will proceed using sequential testing at 5% level with the order as specified below. At any step when the endpoint is not significant at 5% level, the formal testing in subsequent steps will stop; the p-values for the subsequent endpoints in the sequence will be considered exploratory, and hence interpreted at the nominal level. This controls the overall type I error level at 5%, using the closed testing principle. If either of the primary endpoints is not significant, then hypothesis testing for the secondary endpoints will be considered exploratory, and p-values will be interpreted at the nominal level.

For Europe and ROW, the order of testing for secondary endpoints is as follows:

1. Percentage change in liver volume from baseline to Week 52
2. Percentage change in platelet count from baseline to Week 52
3. Change in BFI scale, Item 3 - from baseline to Week 52
4. Change in BPI scale, Item 3 - from baseline to Week 52
5. Change in FACIT-Dyspnea symptom score from baseline to Week 52
6. Change in SRS from baseline to Week 52

In the US, the order of testing for secondary endpoints is as follows:

1. Percentage change in liver volume from baseline to Week 52
2. Percentage change in platelet count from baseline to Week 52
3. Change in BFI scale, Item 3 - from baseline to Week 52
4. Change in BPI scale, Item 3 - from baseline to Week 52
5. Change in FACIT-Dyspnea symptom score from baseline to Week 52

#### **2.4.5.4 Subgroup analyses for the primary endpoints in PAP**

The consistency of the treatment effect in PAP will be evaluated as follows for percentage change from baseline to Week 52 of spleen volume (MN) and percentage change from baseline to Week 52 of % predicted DLco separately:

- Spleen volume by baseline spleen volume severity (severe vs not severe). Severity is defined as baseline spleen volume >15 multiple of normal (MN).
- % predicted DLco by baseline % predicted DLco severity (severe vs not severe). Severity is defined as baseline % predicted DLco <40%.

In addition, for the endpoints of percentage change from baseline to Week 52 of spleen volume (MN), SRS, and % predicted DLco, the consistency of treatment effect in PAP will be assessed by the following subgroups:

- Baseline ALT or AST abnormality (ALT or AST  $\geq$ 1 ULN vs ALT and AST <1 ULN)
- Baseline total bilirubin abnormality (total bilirubin  $\geq$ 1.5 ULN vs total bilirubin <1.5 ULN)

For the percentage change from baseline to Week 52 of spleen volume (MN), whether or not the presence of portal hypertension has an effect on olipudase alfa treatment will be assessed by the following subgroup:

- Presence vs absence of portal hypertension at baseline (detected signs of portal vein hyperpressure is “likely severe portal hypertension” or “likely portal hypertension” for presence of portal hypertension vs detected signs of portal vein hyperpressure is “unlikely portal hypertension” for absence of portal hypertension)

Descriptive summaries on the observed values, change from baseline and percent change from baseline to Week 52 of spleen volume (MN) for patients with severe portal hypertension at baseline will be provided as well if there are at least 3 patients identified with severe portal hypertension at baseline. If the number of patients with severe portal hypertension at baseline is low (<3), only individual patient data will be provided in listings.

Due to the small sample size in these subpopulations, treatment difference within the subgroup will be difficult to interpret. Therefore, the focus of these analyses will be on assessment of interaction between subgroups and the treatment.

For each subgroup, same MMRM models for the primary efficacy endpoints using data from the specific subgroup only will be conducted to provide estimate of treatment effect within each

subgroup. The summary plots of the LS means from the MMRM of the percentage change in DLco (% predicted) and spleen volume (MN) from baseline up to Week 52 with 95% CIs by subgroups will be provided.

To assess the interactions between subgroup and treatment, the same MMRM models for the primary efficacy endpoints described in [Section 2.4.5.1](#) will be applied with the addition of subgroup, subgroup-by-visit interaction, subgroup-by-treatment interaction, subgroup-by-treatment-by-visit interaction. The p-value for overall subgroup-by-treatment interaction, subgroup-by-treatment-by-visit interaction, subgroup-by-visit interaction as well as the p-value for subgroup-by-treatment interaction at week 52 will be provided.

#### **2.4.5.5 Responder analyses for the primary endpoints in PAP**

For the responder analyses specified below, binary measure of responder (yes vs no) at Week 52 will be analyzed with logistic regression including treatment and baseline as covariates. Patients who had missing data at Week 52 will be counted as non-responder. Number and % of responder, as well as odds ratio, 95% CI and p-value from the logistic regression model will be provided.

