### 1.3 DETERMINATION OF SAMPLE SIZE

The sample size calculations are based on the 2 primary efficacy endpoints:

1. Percentage change in DLco (expressed as % predicted of normal) from baseline to Week 52
2. a) For Europe and the rest of the world (ROW) outside of USA: the percentage change in spleen volume (expressed in multiples of normal [MN] ) from baseline to Week 52  
  
b) For US: the combination spleen endpoint which consists of two components: the percentage change in spleen volume (expressed in MN) from baseline to Week 52 and change in splenomegaly-related score from baseline to Week 52.

Although the multiplicity adjustments in statistical testing of hypotheses ensures the study to be positive if only one of the two primary endpoints is significant ([Section 2.4.5.3](#)), each endpoint has been powered adequately in order to choose the sample size for the study as 36 randomized patients in 1:1 ratio in placebo and olipudase alfa treatment arms.

Endpoint	Null hypothesis	Assumptions			Signif. level	Sample Size N	Power
		Trt Diff	SD	Non-evaluable			
DLco	There is no difference between olipudase alfa group and placebo group in percentage change from baseline in percent predicted DLco from baseline to Week 52.	25%	20%	11%	0.05	36	0.93
Spleen Volume	There is no difference between olipudase alfa group and placebo group in percentage change from baseline in spleen volume in multiples of normal from baseline to Week 52.	30%	11.8%	11%	0.05	36	0.99
SRS	There is no difference between olipudase alfa group and placebo group in change from baseline in SRS from baseline to Week 52.	8	9.4	11%	0.15	36	0.82

The following assumptions for the DLco endpoint are based on results obtained from the olipudase alfa Phase 1b study DFI13412:

- A 20% common standard deviation
- A 25% mean difference from baseline to Week 52 between olipudase alfa and placebo in percentage change in DLco (in % predicted)
- An expected exclusion rate from the primary analysis due to non-availability of results at Week 52 is 11%

Based on these assumptions, a comparison between the olipudase alfa arm and the placebo arm will have 93% power using a t-test at a 2-sided 5% significance level and with 36 patients randomized 1:1 to placebo and olipudase alfa.

The assumptions for the spleen volume endpoint are the following:

- An 11.8% common standard deviation based on data from previous ASMD and Gaucher disease Type 1 studies

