- A 30% mean difference from baseline to Week 52 between olipudase alfa and placebo in percentage change in spleen volume (MN)
- An expected exclusion rate from the primary analysis due to non-availability of results at Week 52 is 11%

Based on the above assumptions, a comparison between olipudase alfa and placebo will have over 99% power using a t-test at a 2-sided 5% significance level with 36 patients randomized 1:1 to placebo and olipudase alfa. At 2.5% significance level, the power will still be over 99%.

The assumptions for the splenomegaly-related score endpoint came from the Sanofi-sponsored clinical trial in myelofibrosis (JAKARTA, NCT# 01437787). The assumptions for the power calculations are the following:

- A common standard deviation of 9.4
- A mean difference of 8.0 from baseline to Week 52 between olipudase alfa and placebo in the SRS score
- An expected exclusion rate from the primary analysis due to non-availability of results at Week 52 is 11%

Based on the above assumptions, a comparison between olipudase alfa and placebo will have 82% power using a t-test to detect a statistical trend, defined as 2-sided p-value  $\leq 0.15$ , with 36 patients randomized 1:1 to placebo and olipudase alfa.

Using the simplifying assumption that the 2 components of the combination spleen endpoint are independent, the likelihood that statistical significance will be declared for the combination spleen endpoint is greater than 80%.

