##### ***Responder analyses for spleen volume***

In addition to evaluating the percent change from baseline, a responder analysis will be performed to assist in the interpretation of a clinically meaningful result. In Gaucher disease, therapeutic goals for splenomegaly include reduction in spleen volume of 30-50% within year 1 of enzyme replacement therapy (21). Therefore a responder analysis will be performed, setting the threshold for response at  $\leq -30\%$  change from baseline in spleen volume at 52 weeks.

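### The spleen-volume responder analysis has no rule for a placebo arm without responders; if placebo spleens change by about 0 on average, that is the likely result and the odds ratio would be infinite

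*SAP*

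**What the plan says.** SAP 2.4.5.5 sets one method for the responder analyses: the "binary measure of responder (yes vs no) at Week 52 will be analyzed with logistic regression including treatment and baseline as covariates". On missing values it says: "Patients who had missing data at Week 52 will be counted as non-responder". Besides the number and percentage of responders, the "odds ratio, 95% CI and p-value from the logistic regression model will be provided".

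For spleen volume the stated purpose is that "a responder analysis will be performed to assist in the interpretation of a clinically meaningful result", and the cut-off is a change from baseline of −30% or lower at Week 52.

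The section does not name the estimator, the type of confidence interval or the type of test, and does not say what to do if one arm has no responders. The SAP does give contingency rules elsewhere. Section 2.4.5.1 lists covariance structures to try in order if the MMRM does not converge. Section 2.4.5.4 replaces summaries by listings when fewer than 3 patients have severe portal hypertension. Section 2.6.6 covers only the pattern-mixture analysis.

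**The concern.** The sample-size section plans a 30-point difference in percentage change, and the responder cut-off is also 30 points below baseline. If placebo spleens do not change on average, the active mean sits on the cut-off and the placebo mean lies about two and a half standard deviations from it. With 18 patients per arm, a placebo arm with no responders is then the expected result.

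With an empty responder cell, maximum-likelihood logistic regression has no finite treatment estimate. Any finite odds ratio or Wald interval that the software printed would only show where the iterations stopped. The analysis meant to help readers judge whether the spleen result is clinically meaningful would then lack its promised odds ratio and two-sided interval. A replacement chosen after unblinding would be post hoc.

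**Working it through.** **Inputs from the documents.** SD: "An 11.8% common standard deviation based on data from previous ASMD and Gaucher disease Type 1 studies" (SAP 1.3). Difference 30 percentage points and 11% without a Week 52 result (SAP 1.3). 36 patients randomised 1:1, so 18 per arm (SAP 1.3 and 1.4). Cut-off −30%, with missing counted as non-response (SAP 2.4.5.5).

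**Assumptions not in the documents.** Changes are normally distributed, and the placebo mean change is 0 (range examined: −10% to +5%).

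**The plan's own figures first.** 18 × 0.89 ≈ 16 evaluable per arm. A two-sample t-test with 16 per arm gives power above 0.999 for spleen volume at both 0.05 and 0.025 (SAP: over 99%), 0.928 for DLco (SAP: 0.93) and 0.823 for SRS (SAP: 0.82). The inputs are therefore read as the SAP intends.

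**Chance of no placebo responder.**
- Placebo response probability among evaluable patients: Φ(−30/11.8) = Φ(−2.54) = 0.0055.
- With 11% set to non-response: (1 − 0.89 × 0.0055)^18 = 0.915. With none missing: (1 − 0.0055)^18 = 0.905.
- Active arm, mean −30%: response probability 0.5, so 18 × 0.89 × 0.5 = 8.0 responders are expected. The chance of at least one is 1 − (1 − 0.445)^18 > 0.9999.

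| Placebo mean | Placebo response probability | P(0/18 placebo responders), 11% missing |
|---|---|---|
| +5% | 0.0015 | 0.98 |
| 0 | 0.0055 | 0.92 |
| −5% | 0.0171 | 0.76 |
| −10% | 0.0451 | 0.48 |

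**Break-even.** For the chance to fall to one half, each patient's probability must be 1 − 0.5^(1/18) = 0.0378, or 0.0378/0.89 = 0.0425 among evaluable patients, so z = −1.72. This needs a placebo mean of −30 + 1.72 × 11.8 = −9.7%, or, at mean 0, an SD of 30/1.72 = 17.4%. At mean 0 and SD 15% the chance is 0.69.

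**What the model gives for 8/18 versus 0/18.**
- *Maximum likelihood.* The odds ratio is (8 × 18)/(10 × 0), which is infinite. A baseline covariate does not cure this: in an illustrative fit with a simulated baseline, the treatment coefficient was 4.9, 9.0, 13.0, 21.0 and 29.0 at iterations 4, 8, 12, 20 and 28, its standard error rose from 3.2 to 511,106, and the Wald p-value moved from 0.12 to 1.0.
- *Likelihood ratio, no covariate.* The null log-likelihood is 8 ln(8/36) + 28 ln(28/36) = −19.07. The alternative is 8 ln(8/18) + 10 ln(10/18) = −12.37. Twice the difference is 13.4, p = 0.00025. The profile interval runs from 5.9 to infinity.
- *Firth, no covariate.* This is equivalent to adding one half to each cell: (8.5 × 18.5)/(10.5 × 0.5) = 30. The profile penalised-likelihood interval is 3.2 to about 4000, penalised likelihood-ratio p = 0.001.
- *Fisher's exact test.* 2 × C(18,8)/C(36,8) = 2 × 43,758/30,260,340 = 0.003.
- *Risk difference.* 8/18 − 0/18 = 44 points, exact unconditional 95% interval about 20 to 69.

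**Chance of p < 0.05 at placebo mean 0** (exact enumeration of all tables, no covariate): Wald 6%, Fisher 94%, Firth penalised likelihood ratio 98%, ordinary likelihood ratio 99%. Simulation with a baseline covariate gave 5.6% for Wald, 96.2% for penalised and 98.5% for ordinary likelihood ratio.

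**SRS for comparison** (SD 9.4, placebo mean 0 assumed): Φ(−12.5/9.4) = 0.092 gives a chance of no placebo responder of 0.22 at the primary threshold. Φ(−18/9.4) = 0.028 gives 0.64 at the secondary one.

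**The case against.** The SAP says only logistic regression. It does not commit to unpenalised estimation or to Wald output, so a penalised fit could be chosen within its wording. Even the ordinary model yields something reportable: counts, percentages, a likelihood-ratio p-value of 0.00025 and an interval from 5.9 upwards. Firth adds little beyond a finite number, since an upper limit near 4000 tells a reader hardly more than infinity and its lower limit drops to 3.2. Its p-value has no power advantage, and its exact type I error reaches 6.4 to 6.5% when both arms respond at 44.5 to 50%. The 0.92 rests on an unstated placebo mean and on a normal tail; t-distributed changes with 3 to 5 degrees of freedom and the same SD bring it to about 0.83 to 0.84. No decision hangs on the analysis, which lies outside the testing procedure of SAP 2.4.5.3.

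Much of this stands, and it is why the point is minor. The open wording does not remove the gap: leaving estimator, interval and test unnamed means choosing them once the empty cell is known. The promised odds ratio and two-sided interval would still probably be missing. The heavier tails weaken the probability but leave it well above one half. The wide Firth interval is a fair criticism, which is the reason to put the risk difference beside it.

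**Conclusion.** The concern holds as a minor, cheap improvement to a supportive analysis. If the placebo mean change is about 0 and changes are roughly normal, the chance that the planned spleen-volume odds ratio and its upper limit are infinite is about 92%. That chance drops below one half only if the placebo mean is below about −9.7%, or if the SD at mean 0 exceeds about 17.4%. Confidence is medium because the documents do not give the placebo mean. What would be lost is a finite odds ratio and a two-sided interval; with Wald output the p-value would be lost as well. The primary MMRM analysis, the multiplicity procedure and the responder percentages (about 44% versus 0%) are untouched.

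**What to change.** In SAP 2.4.5.5, for the spleen-volume responder analysis, name Firth-penalised logistic regression with treatment and baseline, a profile penalised-likelihood 95% interval and a penalised likelihood-ratio p-value (not Wald) as the model output. Add the risk difference with an exact 95% interval, and Fisher's exact test as a supporting check. Applying the same rule to the other responder models is optional and serves only consistency.

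The cost is one or two sentences and a few lines of code; endpoint, threshold, population and alpha do not change. The drawbacks are less familiar output and a very wide Firth upper limit. The gain is a finite estimate and an interpretable interval, not power. It counts as pre-specification only if made before the PAP data are unblinded; made later, it should be labelled post hoc.

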##### ***Responder analyses for spleen volume***

In addition to evaluating the percent change from baseline, a responder analysis will be performed to assist in the interpretation of a clinically meaningful result. In Gaucher disease, therapeutic goals for splenomegaly include reduction in spleen volume of 30-50% within year 1 of enzyme replacement therapy (21). Therefore a responder analysis will be performed, setting the threshold for response at  $\leq -30\%$  change from baseline in spleen volume at 52 weeks.

##### ***Responder analyses for % predicted DLco***

International guidelines for clinically meaningful changes in DLco have been published for idiopathic pulmonary fibrosis (IPF) including 2017 Spanish IPF guidelines and the 2017 French IPF guidelines indicate a decrease of  $>15\%$  DLCO in absolute values is associated with increased risk of mortality (22, 23). At the same time, the Connective Tissue Disease- associated interstitial lung disease (CTD-ILD) -OMERACT CTD-ILD working group has consensus guideline indicates that a relative 15% change constitutes a clinically meaningful change (24).

In addition, Pelligrino et al (25), set a clinically meaningful threshold at 10% and similar values in the range of approximately 10-14% has been reported reviewing datasets from larger studies (26, 27).

Therefore, a responder analysis will be performed using a threshold of 15% improvement in DLco from baseline. This means if a patient has a change from baseline on DLco (% predicted)  $\geq 15\%$  at Week 52, then this patient will be a responder.

